### **6.4. Electrocardiograms**

Electrocardiograms (ECGs) will be performed at screening, admission, pre-dose, on dosing days Day 1 in each period (3–6h post-dose, approximate  $C_{max}$ ), and on Day 15 or at the ET visit with all measurements taken within 5 minutes apart. Triplicate ECGs will be measured at pre-dose, and post dose 1hr, 3hr, 6hr, 8hr, 24hr, 48hr, and 72hr post dose (for both doses) triplicates

measurement will be taken within 5 minutes apart. Subjects should be at rest for 10 minutes prior to ECG. For participants that withdraw or are terminated early from the study, ECG will be performed at the ET visit. ECG time points are indicated in the SOA ([Table 1](#)). The date and time of each ECG and its results will be documented in the source documents and transcribed into the eCRF.

## **6.5. Alcohol and Drug Screening**

Participants will undergo urine drug and breath alcohol screening to confirm the absence of alcohol or substances of abuse (including amphetamines, barbiturates, cocaine metabolites, opiates, benzodiazepines, and cannabinoids) at Screening, upon admission to the unit, and at any time during the study as warranted by the Investigator or study staff. In accordance with the exclusion criteria ([Section 4.2](#)) any individual who has a test reflecting recent use of alcohol or illicit substances prior to the first study drug dose must not be enrolled in the study. Analytes for the urine drug test are specified in [Table 4](#).

## **6.6. Screening Serology**

A blood sample for screening serology, including measurement of hepatitis B surface antigen (HbsAg), anti-HCV antibody (Ab), and anti-HIV Ab, is to be collected during Screening. Results must be negative for the participant to be eligible for the study; however, participants with adequately treated HCV (HCV ribonucleic acid negative) are eligible for enrollment.

## **6.7. Vital Signs**

Vital signs, including systolic (SBP) and diastolic blood pressure (DBP), heart rate, respiration rate, and oral temperature (includes height, weight, and BMI at the Screening Visit), are to be measured at the time points indicated in the SOA ([Table 1](#)). Vital signs (except for height and weight) will be monitored periodically during and following study drug administration. The investigator may repeat the vital signs if deemed appropriate.

Participant must be in a rested seated or supine position and in calm state for at least 3 minutes before vital signs are collected. When possible, blood pressure should be taken in the arm not being used for blood sample collections throughout the study, using the same methodology (automated or manual). Repeat measures and more frequent monitoring can be implemented for clinically significant changes in blood pressure or heart rate at the discretion of the investigator or designee.

## **6.8. Safety Laboratory and Pregnancy Testing**

Clinical laboratory testing will be performed at the time points designated in the SOA ([Table 1](#)). Samples for safety laboratory testing are to be collected following a minimum 8-hour fast. Participants will be in a seated or supine position during blood collection. Clinical laboratory testing (hematology with differential, serum chemistry, coagulation, and urinalysis) will be performed using standard methods.

Also, for women, serum human chorionic gonadotropin pregnancy test will be performed at Screening, urine test at the time of admission to the clinic (Day -1), and at Day 15 Discharge or at Early Termination. Laboratory tests are listed in [Table 4](#).

**Table 4: Clinical Laboratory Tests**

Hematology: 
 
• Hematocrit
 
• Hemoglobin
 
• Platelet count
 
• RBC count
 
• WBC count – with differential
 
	Serum Chemistry: 
 
• Glucose
 
• BUN
 
• Creatinine
 
• Total bilirubin
 
• AST
 
• ALT
 
• GGT
 
• Alkaline phosphatase
 
• Creatine kinase
 
• Total protein
 
• Lactate dehydrogenase
 
• Direct bilirubin
 
• Total bilirubin
 
• Sodium
 
• Potassium
 
• Total CO2
 
• Chloride
 
• Calcium
 
• Inorganic phosphate
 
• Magnesium
 
• eGFR
 

Coagulation: 
 
• PT/INR
 
• PTT
 
	
Urinalysis: 
 
• Bilirubin
 
• pH
 
• Specific gravity
 
• Protein
 
• Leukocytes
 
• Urobilinogen
 
• Glucose
 
• Nitrates
 
• Ketones
 
• Blood
 
• Microscopic urine analysis
 
	
Urine Drug Screen: 
 
• Amphetamines
 
• Barbiturates
 
• Opiates
 
• Benzodiazepines
 
• Cocaine metabolites
 
• Cannabinoids
 
	
Pregnancy Testing: 
 
• Serum hCG – at Screening
 
• Urine hCG – at the time of study center admission and Day 15 Discharge or ET
 
	Post-Menopausal Status Testing: 
 
• FSH
 
• Estradiol
 

Alcohol Screening: 
 
• Breath alcohol test
 
	

Abbreviations: ALT = alanine aminotransferase; AST = aspartate aminotransferase; BUN = blood urea nitrogen; CO2 = carbon dioxide; eGFR = estimated glomerular filtration rate; FSH = follicle-stimulating hormone; GGT = gamma-glutamyl transferase; hCG = human chorionic gonadotropin; INR = international normalized ratio; PT = prothrombin time; PTT = partial thromboplastin time; RBC = red blood cell; WBC = white blood cell.

### 6.8.1. Sample Collection, Storage, and Shipping

Biological material will be stored and secured in a way that assures that unauthorized access is prohibited, and the samples are not lost, deteriorated, or accidentally or illegally destroyed. Details for laboratory sample handling, storage, and shipping are provided in the Laboratory Manual.

## 6.9. Dispensing Study Drug

Following Screening and reconfirmation of eligibility at the time of clinic admission, participants will be randomly assigned to a treatment sequence according to the study center's SOPs. Using the randomization schedule, the onsite pharmacist will prepare and deliver the appropriate study drug to the study center for dosing.

## **6.10. Pharmacokinetics**

Fifteen venous blood samples will be withdrawn via an indwelling cannula or by venipuncture at regular time intervals. The exact date and time of PK sample collection is to be documented in the eCRF. Blood samples will be collected prior to and following administration of the single oral dose of neat ARN-75039 in HPMC capsules or ARN-75039 with excipients in tablet form at according to the timepoints listed in the SOA (Table 1). On Day 15 or at ET, the PK blood sample at approximately the same time as the dose of study drug was administered.

## **6.11. Discharge from the Study Center**

Participants are to be discharged from the study center as indicated in the SOA (Table 1).

The actual date and time of discharge from the study center will be collected in the source documents and transcribed into the eCRF.

## **6.12. Adverse and Serious Adverse Events**

### **6.12.1. Definition of Adverse Events**

#### **6.12.1.1. Adverse Event (AE)**

An AE is the development of an undesirable medical condition or the deterioration of a pre-existing medical condition following or during exposure to a pharmaceutical product, whether or not considered causally related to the product. In clinical studies, an AE can include an undesirable medical condition occurring at any time, including baseline or washout periods, even if no study treatment has been administered.

All AEs that occur after the start of study drug administration through the EOS visit following the cessation of treatment, whether or not they are related to the study, must be recorded in the eCRF. Any reported AEs prior to first study drug administration will be documented within the participant's medical history.

#### **6.12.1.2. Serious Adverse Event (SAE)**

A serious adverse event (SAE) is an AE occurring during any study phase (i.e., baseline, treatment, washout, or follow-up), and at any dose of the investigational product, comparator or placebo, that fulfils one or more of the following:

- Results in death
- Is life-threatening

The term "life-threatening" in the definition of "serious" refers to an event in which the participant was at risk of death at the time of the event. It does not refer to an event, which hypothetically might have caused death, if it were more severe.

- Requires inpatient hospitalization or prolongation of existing hospitalization

In general, hospitalization signifies that the participant has been detained (usually involving at least an overnight stay) at the hospital or emergency ward for observation and/or treatment that would not have been appropriate in the physician's office or

outpatient setting. Complications that occur during hospitalization are AEs. If a complication prolongs hospitalization or fulfills any other serious criteria, the event is serious. When in doubt as to whether “hospitalization” occurred or was necessary, the AE should be considered serious.

Hospitalization for elective treatment of a pre-existing condition that did not worsen from baseline is not considered an AE.

- Results in persistent disability/incapacity

The term disability means a substantial disruption of a person’s ability to conduct normal life functions.

This definition is not intended to include experiences of relatively minor medical significance such as uncomplicated headache, nausea, vomiting, diarrhea, influenza, and accidental trauma (e.g., sprained ankle) which may interfere with or prevent everyday life functions but do not constitute a substantial disruption.

- Is a congenital anomaly/birth defect
- Is otherwise considered as medically important

Important medical events that may not result in death, be life threatening, or require hospitalization may be considered an SAE when, based upon appropriate medical judgment, they may jeopardize the participant and may require medical or surgical intervention to prevent one of the outcomes listed in this definition. Examples of such medical events include blood dyscrasias or convulsions that do not result in participant hospitalization, or the development of drug dependency or drug abuse.

All SAEs that occur after the start of study drug administration through the end of study (EOS) visit following the cessation of treatment, whether or not they are related to the study, must be recorded in the eCRF and other applicable databases.

#### **6.12.1.3. Unexpected Adverse Drug Reactions**

An unexpected adverse drug reaction (ADR) is a reaction for which the nature or severity is not consistent with the applicable product information (Investigator’s Brochure). Until product information is amended, expedited reporting is required for additional occurrences of the reaction. Reports that add significant information on specificity or severity of a known, already documented SAE constitute unexpected events. For example, an event more specific or more severe than described in the Investigator's Brochure would be considered “unexpected.” Specific examples would be (a) acute renal failure as a labeled ADR with a subsequent new report of interstitial nephritis and (b) hepatitis with a first report of fulminant hepatitis.

#### **6.12.1.4. Abnormal Laboratory Values**

Any abnormality in a laboratory value that is new in onset or which has worsened in severity or frequency from the baseline condition and meets 1 of the following criteria will be recorded on the AE pages of the eCRF:

- Requires therapeutic intervention or diagnostic tests.
- Leads to discontinuation of investigational product.

- Has accompanying or inducing symptoms or signs.
- Is judged by the Investigator as clinically significant.

#### **6.12.1.5. Treatment-Emergent Adverse Events (TEAE)**

An AE will be considered treatment-emergent if the onset date and time is after study drug administration or if the AE is present at baseline but worsens in intensity or is subsequently considered drug-related by the Investigator after study drug administration.

#### **6.12.2. Relationship to Study Drug**

The Investigator must use his/her medical judgment to assess the relationship of the TEAE to study drug. Even if the Investigator feels there is no relationship to study drug, the TEAE is to be reported.

- Not Related: A TEAE that does not follow a reasonable temporal sequence from administration of the study drug, or that could be reasonably explained by other factors, including underlying disease, complications, concomitant drugs, or concurrent treatment.
- Unlikely Related: A TEAE that is doubtfully related to administration of the study drug because the establishment of a causal relationship is considered biologically and physiologically highly improbable, though it may follow a reasonable temporal sequence from administration of study drug.
- Possibly Related: A TEAE that follows a reasonable temporal sequence from administration of the study drug (including the course after withdrawal of the study drug), that could not exclude the possibilities of the study drug (e.g., existence of similar reports attributed to the suspected study drug and its analogues, reactions attributable to the pharmacological effect), although other factors such as underlying disease, complications, concomitant drugs, or concurrent treatment are presumable.
- Probably Related: A TEAE that follows a reasonable temporal sequence from administration of the study drug (including the course after withdrawal of the study drug), and that could exclude the possibilities of factors, such as underlying disease, complications, concomitant drugs, or concurrent treatment, other than the study drug.
- Definitely Related: A TEAE considered to be undeniably related to the administration of study drug. Factors to be taken into consideration when assigning a definite relationship include whether the TEAE:
  - Follows a clear temporal sequence compared to administration of study drug.
  - Could not be possibly explained by the known characteristics of the participant's clinical state, environmental or toxic factors, or other modes of therapy administered to the participant.
  - Disappears or decreases on cessation or reduction in dose of study drug.
  - Reappears or worsens when study drug is re-administered.
  - Follows a response pattern known to be associated with administration of study drug.

If no valid reason exists for suggesting a relationship, then the AE should be classified as “unrelated.” If there is any valid reason, even if undetermined, for suspecting a possible cause-and-effect relationship between the investigational product and the occurrence of the AE, then the AE should be considered “related.”

If the relationship between the AE/SAE and the investigational product is determined to be “possible,” “probable,” or “definite,” the event will be considered to be related to the investigational product for the purposes of expedited regulatory reporting.

### **6.12.3. Severity**

The intensity of each AE is to be assessed by the Investigator according to the National Cancer Institute Common Terminology Criteria for Adverse Events (NCI CTCAE), Version 5.0:

- ([https://ctep.cancer.gov/protocoldevelopment/electronic\\_applications/docs/CTCAE\\_v5\\_Quick\\_Reference\\_5x7.pdf](https://ctep.cancer.gov/protocoldevelopment/electronic_applications/docs/CTCAE_v5_Quick_Reference_5x7.pdf)).

If the AE is not included in the NCI CTCAE, then the Investigator is to determine the intensity of the AE according to the following criteria:

- Grade 1: Mild (awareness of sign or symptom, but easily tolerated)
- Grade 2: Moderate (discomfort sufficient to cause interference with normal activities)
- Grade 3: Severe (incapacitating, with inability to perform normal activities)

It is important to distinguish between serious and severe AEs. Severity is a measure of intensity whereas seriousness is defined by the criteria under [Section 6.13.1.2](#). An AE of severe intensity may not be considered serious.

### **6.12.5. Pregnancy**

Should a pregnancy occur in a female participant or the partner of a male participant, it must be reported and recorded on the pregnancy form. Pregnancy in itself is not regarded as an AE unless there is a suspicion that an investigational product may have interfered with the effectiveness of a contraceptive medication.

The outcome of all pregnancies (spontaneous miscarriage, elective termination, normal birth or congenital abnormality) must be documented, and any live births are to be followed for 1 month.

All reports of congenital abnormalities/birth defects are SAEs. Spontaneous miscarriages should also be reported and handled as SAEs. Elective abortions without complications should not be handled as AEs.

#### **6.12.6. Adverse Events of Special Interest (AESI)**

All AEs and SAEs that occur during the study will be reported and investigated.

However, because of observations of tachycardia, early GI symptoms in animal studies (e.g., severe malnutrition due to reduced food consumption and body weight loss observed in rats that received ARN-75039 at doses  $\geq 2\times$  the NOAEL), and skin symptoms (e.g., grade 2 pruritus), subjects in this study should be monitored for any new onset or worsening of elevated heart rate, GI and skin-related signs and symptoms.

An AESI may be serious or nonserious (e.g., meeting regulatory criteria definition). Such events will require further investigation to better characterize and understand them. Even if not meeting the “seriousness” criteria to be reported as SAE, these events must be assessed for severity per [Section 6.13.3](#) and relationship to study drug similarly as for SAEs ([Section 6.13.2](#)).

Any AESI deemed as related (e.g., definitely, probably, or possibly), greater than grade 1 or severe (if not included in the NCI CTCAE) may require discontinuation of dosing of ARN-75039 (and follow-up until resolution) per the discretion of the Investigator and Sponsor Medical Monitor.

#### **6.12.7. Reporting Serious Adverse Events**

Each AE will be assessed to determine whether it meets seriousness criteria ([Section 6.13.1.2](#)).

If the AE is considered serious, the Investigator should report this event to the Sponsor’s Medical Monitor as outlined below and, also, to the Institutional Review Board (IRB) according to its SOPs.

If the Investigator detects an SAE in a study participant after the last scheduled follow-up visit, and considers the SAE related or possibly related to prior study treatment, the Investigator should report it to the Sponsor’s Medical Monitor.

All information about SAEs will be collected and reported via participant report, relevant source document request and review, and SAE report entry within the eCRF. (Participant and Sponsor’s Medical Monitor contact information will be contained in the investigational site file.) The Investigator should send the initial SAE report to the Sponsor’s Medical Monitor within 24 hours of becoming aware of the SAE. At minimum, the initial SAE report should include the following information:

- Event
- Study code
- Participant number, initials, and date of birth
- Investigational product
- Reporter name and contact information

In the case of a “minimum report” (one that solely comprises the information bulleted above), a more detailed follow-up report should be sent as soon as more information becomes available but no later than 7 calendar days after the date of the initial report. Each SAE should be followed up until resolution or stabilization and for reported deaths, the Investigator should supply the Sponsor’s Medical Monitor and the IRB with any additional requested information (e.g., autopsy reports, terminal medical reports).

The original SAE form and relevant source documents should be kept at the study site. The Sponsor, or its designee, will be responsible for determining reporting timelines and reporting SAEs to regulatory authorities according to the applicable regulatory requirements.

SAEs that are ongoing at the Follow-up visit should be followed until resolved.

Arisan, or qualified designee, is responsible for notifying the relevant regulatory authorities of certain events. It is the Principal Investigator’s responsibility to notify the IRB of all SAEs that occur at his or her site. Investigators will also be notified of all unexpected, serious, drug-related events (7/15 Day Safety Reports) that occur during the clinical trial. The study site is responsible for notifying its IRB of these additional SAEs.

### **6.13. Concomitant Medication Assessments**

All prescription and OTC medications, herbals, and supplements taken by participants during the study (i.e., from signing the ICF through the Day 15 visit) must be documented on the source document and transcribed into the eCRF.

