- **End of Active Treatment (Day 15 Discharge Visit or Early Termination Visit):** Upon successful completion of active treatment, participants will be discharged from the study site on Day 15. The Day 15 Discharge Visit will include the completion of safety assessments, such as a physical examination, vitals, ECG recording, adverse event review, and clinical laboratory tests. Participants who complete both dosing days will be encouraged to complete all study visits. Participants who do not complete all study visits or terminate early from the study will be asked to complete the Early Termination Visit within 1 day after withdrawal from the study.
- **Day 36 Telephone Follow Up Phone Call:** Participants will be contacted by phone on Day 36—i.e., 28 days following the last study dose administered on Day 8. The purpose of this follow-up call is to assess for any adverse events.

If a participant has a study drug-related Grade > 1 TEAE during the Treatment Period, study drug dosing may be discontinued for that participant following discussion between the Investigator and Sponsor Medical Monitor. These participants will not be replaced. If a subject has a study drug-related Grade 1 TEAE during the Treatment Period, study drug dosing may also be discontinued for that subject per the Investigator's discretion. However, these subjects may be replaced at the Sponsor's discretion. Discontinued participants experiencing a study drug-related TEAE will be asked to complete follow up study visits through the Day 36 Phone Call Follow Up.

If a participant terminates early for a reason other than a study drug-related TEAE during the Treatment Period, the participant may be replaced. These participants will also be asked to complete follow up study visits through the Day 36 Phone Call Follow Up, unless they terminated their participation in the study prior to dosing. Study drug dose level modifications or dosing administration deviations outside the protocol-specified windows are not permitted during the Treatment Period.

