#### **4.2. Participant Exclusion Criteria**

Participants meeting any of the following criteria are not eligible for study participation:

1. Any clinically significant underlying illness in the opinion of the Investigator.
2. Poor venous access.
3. Prior exposure to ARN-75039.
4. History of drug or alcohol abuse within 1 year of Screening in the opinion of the investigator, or a positive test for drugs of abuse or alcohol at Screening or Day -1.
5. Use of any prescription or over-the-counter (OTC) medications, including food supplements, vitamins, herbal medications (e.g., St. John's wort), and cannabis, with the exception of contraceptive medications and as needed (prn) acetaminophen or paracetamol (not exceeding 2 grams/day) within 7 days prior to study drug administration and through the Day 15 Discharge visit.
6. Any female who is pregnant or breastfeeding, or any female who is planning to become pregnant during the study and safety follow-up period.
7. Currently enrolled in another investigational device or drug study, or less than 30 days or 5 half-lives of the prior investigational agent (whichever is longer) or plans to enroll in another investigational device or drug study during the course of this study.
8. Inability to ingest all capsules of a multi-capsule dose within 5 minutes of ingestion of the first capsule.
9. Positive serology for hepatitis B virus (HBV), hepatitis C virus (HCV), or human immunodeficiency virus (HIV) at Screening; participants with adequately treated HCV are eligible for enrollment.
10. Consumption of Seville oranges, grapefruit or grapefruit juice within 72 hours prior to Day 1 or during the study.
11. History of malignancy, except adequately treated basal cell carcinoma or in situ carcinoma of the uterine cervix.

12. Smoking cigarettes, cigars, cigarillos or E-cigarettes
13. Any reason or condition that, in the investigator's opinion, may compromise study participation, present a safety risk to the participant, or may confound the interpretation of the study results.
14. A QT duration corrected for heart rate by Fridericia's formula (QTcF) > 450 millisecond (msec) based on either single or averaged QTcF values of triplicate ECGs obtained over a 3-minute interval (at Screening).
15. Blood product (including plasma) donation within 30 days before Screening.
16. Unwilling to consume a breakfast on study drug administration days.
17. History of:

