## **5.6. Concomitant Medications**

### **5.6.1. Prohibited Medications**

The following concomitant therapies are prohibited:

- Use of any prescription or OTC medications, including GLP-1 agonists (e.g., prescribed for weight management), food supplements, vitamins, herbal medications (e.g., St. John's wort), and cannabis, with the exception of contraceptive medications and as needed (prn) acetaminophen (also known as paracetamol) (not exceeding 2 grams/day) within 7 days prior to study drug administration and through the Day 15 visit.
- Any investigational drug or device within 30 days or 5 half-lives of the drug, whichever is the longer, prior to Day 1 and through the Day 15 visit.

If deemed necessary by the Investigator, medications for TEAEs may be administered regardless of relationship to treatment with study drug. All concomitant medications taken in conjunction with a TEAE will be recorded in the source documents and in the eCRF.

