4.5 Prior and Concomitant Medications

All prescription and over-the-counter (OTC) medications, herbals, and supplements taken by participants during the study (i.e., from signing the informed consent form (ICF) through the Day 15 visit) must be documented on the source document and transcribed into the eCRF.

Any medications prohibited in the protocol should not be allowed and will result in the subject being violated by protocol for the PK population. Refer to the protocol for any additional information.

Prior and concomitant medications will be recorded and coded using the current version of WHO Drug Enhanced Dictionary (Global B3 September 2024 or higher). Prior medications will be those that start and end prior to the first dose of study drug.

Concomitant medications will be those that have a known end date after the first dose of study drug or have a missing end date. Any concomitant medication taken during the washout period will be assigned to the prior treatment given. Anatomical Therapeutic

Chemical (ATC) classification and Preferred Term will be assigned to each record of prior or concomitant medication. All prior and concomitant medications will be listed by subject and by treatment sequence (both prior and concomitant), and treatment (for concomitant), including ATC classification (level 3), preferred term and reported term, the start and end dates (or ongoing status), dose, unit, frequency, route of drug administration, and indication. All concomitant medications administered will be presented in a data listing.

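### Routine concomitant-medication recording stops at Day 15 while the protocol assesses adverse events to Day 36, so for 21 days the causality of late events is less well documented

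*Protocol*

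**What the plan says.** **Medication recording.** Protocol 6.13 sets the recording period as "from signing the ICF through the Day 15 visit"; SAP 4.5 sets it as "from signing the informed consent form (ICF) through the Day 15 visit". In Table 1 of both documents, concomitant medications are marked at Screening, Admission, Discharge and Early Termination (ET), and nowhere later.

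**Medication ban.** Protocol 5.6.1 prohibits nearly all prescription, over-the-counter, supplement and herbal products "within 7 days prior to study drug administration and through the Day 15 visit". Exclusion criterion 5 carries the same end point. Participants stay on site until Day 15.

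**Event-triggered recording.** Section 5.6.1 first allows medication to be given for treatment-emergent events (TEAEs). It then adds: "All concomitant medications taken in conjunction with a TEAE will be recorded in the source documents and in the eCRF". No end date is attached.

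**Adverse events.** Table 1 of both documents marks adverse events at the Day 36 call, and protocol 3.1 says of it: "The purpose of this follow-up call is to assess for any adverse events". Protocol 6.12.1.1 and 6.12.4 collect events to an EOS visit that is never given a study day. Protocol 6.12.1.5 defines a TEAE with no upper time limit. SAP 4.7.2 documents adverse events, and counts them as treatment-emergent, only to about 7 days after the last dose.

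**Causality.** Protocol 6.12.2 rests the assessment on the investigator's medical judgment. Its categories refer to concomitant drugs: Probably Related, for example, is for an event "that could exclude the possibilities of factors, such as underlying disease, complications, concomitant drugs".

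**The concern.** Three things end together at Day 15: confinement, the ban and routine recording. Medications are therefore recorded while new exposures are least likely, and recording stops when they become likely. The protocol still looks for adverse events for three more weeks and asks the investigator to weigh concomitant drugs when assigning causality.

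Late events are plausible. Protocol 3.2 acknowledges a long half-life and a relatively short washout. Section 1.2.3 notes a potential phototoxic risk, and section 6.12.6 lists skin and gastrointestinal symptoms among the events of special interest. For a rash reported on Day 36, a product started after discharge is an obvious competing explanation, and no scheduled question asks about it.

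At stake is how well the related/not related decision is supported for such an event. That decision also matters outside the tables, because 6.12.2 treats possible, probable and definite relationships as related for expedited regulatory reporting.

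**Working it through.** The check is study-day arithmetic plus a comparison of sections.

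**Inputs**
- Last dose: Day 8 (protocol 3.1).
- Follow-up call: 28 days after that dose, window ±2 days (protocol 3.1 and Table 1).
- End of routine medication recording: Day 15 (protocol 6.13, SAP 4.5).
- End of the medication ban: Day 15 (protocol 5.6.1).
- SAP adverse-event and TEAE window: about 7 days after the last dose (SAP 4.7.2).

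**Reproducing the plan's own dates**
- Day of the call: 8 + 28 = Day 36, as stated.
- Total duration: 21 days of screening + 36 = 57 days, as stated.

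**The gap**
- Day 36 − Day 15 = 21 days (Days 16 to 36).
- With the window: 34 − 15 = 19 to 38 − 15 = 23 days.
- Share of the 28 days after the last dose: 21/28 = 75%.
- Share of Days 1 to 36: 21/36 = 58%.
- For a participant who terminates early, the last scheduled medication check is the ET visit, yet Table 1 note a still requires the Day 36 call. That gap can exceed 21 days.

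These are shares of calendar time. The documents give no basis for predicting how many events will fall in the gap.

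**What still captures medications after Day 15**
- Protocol 5.6.1 is triggered by an event. Because it follows a sentence about treating TEAEs, it can be read as covering only treatment and so miss a drug started before the event. The wording does not settle this.
- Protocol 6.12.7 gathers participant reports and source documents for serious events, but concomitant drugs are not among the items listed for the minimum initial report.
- For a late non-serious event, nothing requires a systematic medication history.

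**What the SAP would do with a late event**
- SAP window: 8 + 7 = about Day 15.
- An event starting well after Day 15 is outside the SAP's TEAE definition and would not enter its TEAE tables.
- Under the protocol's definition the same event is treatment-emergent. The SAP's own Table 1 also marks adverse events at the Day 36 call, so SAP 4.7.2 disagrees with both.

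**After the change:** with recording extended to the call, the gap falls from 21 days to 0.

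**The case against.** A reader might infer that causality of late events cannot be judged under the protocol's own definitions. The documents do not support that. Section 6.12.2 relies on medical judgment and does not confine the investigator to medications in the eCRF, so the investigator can ask when an event is reported. The categories also tolerate uncertainty: Possibly Related applies even where another drug is a presumable cause. For events soon after Day 15, the preceding history is already recorded.

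A reader might also infer that late events would distort the related/not related split in the secondary-endpoint tables. Under SAP 4.7.2 as written they would not reach those tables. Concomitant medications are only listed (protocol 7.7, SAP 4.5), and the primary PK comparison does not use them.

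Nor do protocol 5.6.1 and 6.13 necessarily contradict each other. One can be read as event-triggered and the other as routine recording for everyone, and both can be followed. The phrase in 5.6.1 is also broad enough to include a drug that preceded the event.

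All of this stands and limits the point. It does not remove it. The broad reading of 5.6.1 is possible but not stated, and no medication question is scheduled at the call. The SAP window keeps late events out of the tables only by departing from the protocol. Expedited-reporting decisions do not depend on the SAP window at all.

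**Conclusion.** The point holds in a limited form. For Days 16 to 36 (21 days, 19 to 23 with the window) the protocol assesses adverse events without routine medication recording, in the period when the ban and confinement no longer apply. Causality of late events is less well documented than it could be, though still judgeable. As written, the effect on the secondary-endpoint tables is limited, because SAP 4.7.2 closes at about Day 15. That cut-off is itself inconsistent with the Day 36 assessment and with the protocol's open-ended TEAE definition.

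The conclusion assumes that the Day 36 call is the end of adverse-event collection, as Table 1 and protocol 3.1 indicate; the EOS visit is not defined well enough to confirm it. The number of events affected is unknown and may be zero among 16 participants. This is a low-severity point, worth acting on because the remedy is cheap.

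**What to change.** 1. Mark concomitant medications in the Day 36 column of Table 1 in both documents.
2. Extend the recording period in protocol 6.13 and SAP 4.5 to the Day 36 call. Leave the prohibition period as it is.
3. State in protocol 5.6.1 that event-triggered recording covers any medication taken before or during the event, not only its treatment.
4. Tie the EOS visit in protocol 6.12.1.1 and 6.12.4 to the Day 36 call, and align SAP 4.7.2 with it, so that adverse-event collection, the TEAE window and medication recording share one end date. Steps 1 and 2 alone would collect medications for a period that SAP 4.7.2 still leaves out.

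**Cost:** one more question in a call already scheduled, with minor data entry and coding for 16 participants, plus the text changes above. No visit or sample is added, and the PK analysis is untouched.
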